### **8.13.1 Intensity of Adverse Events**

The intensity of the AEs will be graded according to CTCAE version 4. For any adverse event that is not specifically covered in CTCAE version 4, the following criteria should be used:

---

Grade	Description
1	Mild; asymptomatic or mild symptoms; clinical or diagnostic observations only; intervention not indicated
2	Moderate; minimal, local or noninvasive intervention indicated; limiting age-appropriate instrumental activities of daily living
3	Severe or medically significant but not immediately life-threatening; hospitalization or prolongation of hospitalization indicated; disabling; limiting self-care activities of daily living
4	Life-threatening consequences; urgent intervention indicated.
5	Death related to AE

If the intensity (Grade) changes within a day, the maximum intensity (Grade) should be recorded. If the intensity (Grade) changes over a longer period of time, the changes should be recorded as separate events (having separate onset and stop dates for each grade).

### **8.13.2 Test Medication Causality**

The relationship (or association) of each AE to the test medication will be assessed by the investigator according to the following definitions:

**Unrelated:** There is no chance that the study medication caused the AE; other conditions, including concurrent illnesses, progression or expression of the disease state, or a reaction to a concomitant medication best explain the event.

**Unlikely:** There is little chance that the study medication caused the AE; other conditions, including concurrent illnesses, progression or expression of the disease state, or a reaction to a concomitant medication best explain the event.

**Possible:** The association of the AE with the study medication is unknown; however, the AE is not clearly due to another condition.

**Probable:** A reasonable temporal association exists between the AE and treatment administration and, based on the investigator's clinical experience, the association of the AE with the study treatment seems likely.

**Definite:** The association of the AE with the study medication has a direct relationship.

For the purpose of safety analyses, all AEs which are classified as "Possible," "Probable" or "Definite" will be considered treatment-related events.

### **8.13.3 Serious Adverse Events**

A **serious adverse event (SAE)** is defined as any experience that suggests a significant clinical hazard, contraindication, side effect, or precaution. This includes any event which:

- Results in death.
- Is life-threatening.
- Requires inpatient hospitalization or causes prolongation of existing hospitalization
- Results in persistent or significant disability/incapacity.
- Results in congenital abnormality/birth defect.
- Requires intervention to prevent permanent impairment or damage

An SAE also may include other events, based on medical judgment, which jeopardize the patient or subject and require medical or surgical intervention to prevent one of the outcomes listed above.

Any SAE, including death due to any cause, which occurs during the study or within 30 days following cessation of study medication, whether or not related to the study medication, must be reported immediately via telephone (within 24 hours) to Veru Inc. Drug Safety.

In addition, the investigator must immediately complete a Serious Adverse Event eCRF report form and electronically submit the form. The investigator will promptly notify the Institutional Review Board (IRB).

If additional information regarding a previously submitted SAE is obtained, a follow-up SAE eCRF report should be completed and submitted as indicated above. Supporting source documentation should be provided to Worldwide Clinical Trials Drug Safety at the contact information below.

### **8.13.4 Initial Reports**

SAEs will be collected from the time of first study drug administration through 30 days after receipt of final dose of study drug. SAEs and events of clinical interest must be reported to the Sponsor (or designee) within 24 hours of the knowledge of the occurrence.

In the event an SAE is observed or reported, the SAE report will be completed as thoroughly as possible including all available details about the event and the signature of the Investigator. If the Investigator does not have all information about an SAE, the Investigator will not wait to receive additional information before notifying the Sponsor of the event and completing the form. The form will be updated when additional information is received.

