### **8.1 Clinic Visits**

Potential study participants will visit the clinical research facility as needed for screening evaluations in the 28 days prior to enrollment. Subjects will have study related visits at Day 1, Day 30, Day 60, and 84. A follow-up visit will be conducted approximately 30 days after the last dose.

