## **8.8 Follow-up Visit**

The following assessments will be performed 30 days ( $\pm$  7 days) after the End of Study visit (Day 84):

1. Vital Signs (temperature/pulse/supine blood pressure)
2. Physical examination (including height and weight)
3. Adverse events

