## **8.9 Pharmacokinetic Sampling**

### **8.9.1 Blood Samples**

Samples of venous blood for the determination of trough plasma concentrations of VERU-944 and related metabolites will be obtained on Days 1 (prior to dose), 30, 60 and 84. The sample should be taken prior to dosing with VERU-944 on these days. The time of the last dose of study drug prior to the clinic visit (day before visit) and the time of the blood samples should be carefully recorded.

The blood samples should be collected in a 6 mL K2EDTA blood collection tube at each collection time.

Immediately after collection, the tubes will be gently inverted several times to mix the anticoagulant with the blood sample. Blood samples may be kept on wet ice (the use of ice packs in a water bath is also acceptable) for up to 20 minutes until processed. The plasma fraction will be separated by placing the collection tube into a centrifuge for 10 minutes at 1,500 x g. The plasma fraction will be withdrawn by pipette and divided into two polypropylene freezing tubes (with each tube receiving approximately equal aliquots). All plasma samples will be placed into a freezer at -20°C (or below) within 1 hour after collection. (NOTE: A flash freezing in dry ice or liquid nitrogen is NOT required under this protocol but may be used.)

Any remaining plasma samples after completion of the protocol outlined pharmacokinetic analysis may be used to identify and quantify the metabolites of VERU-944 or measure other biomarkers of safety or efficacy.

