### **8.11 Subject Stopping Rules**

If, in the opinion of the investigator, the participation in the study is or is becoming detrimental to the well-being of a particular subject, this issue should be discussed with the Medical Monitor for this study and dosing may be discontinued.

Subjects that experience a Grade 3 or greater toxicity according to the Common Terminology Criteria for Adverse Events (CTCAE) version 4

([https://evs.nci.nih.gov/ftp1/CTCAE/CTCAE\\_4.03\\_2010-06-14\\_QuickReference\\_5x7.pdf](https://evs.nci.nih.gov/ftp1/CTCAE/CTCAE_4.03_2010-06-14_QuickReference_5x7.pdf)) that is deemed to be possible, probably or definitely related to study drug will be discontinued from the study. Prior to discontinuation from the study, the grading of the event and causal relationship should be discussed with the Medical Monitor for the study.

Subjects will be discontinued from dosing if AST or ALT levels are >5 times the upper limit of normal, or if AST or ALT levels are >3 times the upper limit of normal along with a total bilirubin elevation of >2 times the upper limit of normal.

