**12.2 Appendix B: Schedule of Study Evaluationse**

Day	Screen a	Pre-Randomization during screening period	1	14	30	60	84 End of study	Follow-up
Informed Consent	X							
Medical History	X		X					
Assessment of Eligibility ( For Screening visit capture history of hot flashes frequency and severity )	X	X	X					
Physical Exam	X		X				X	X
Vital signs	X		X	X	X	X	X	X
12-lead ECG (single)	X							
Clinical Laboratory Tests								
Hematology	X		X		X	X	X	
Urinalysis	X		X					
Serum Chemistry	X		X	X	X	X	X	
Serum Hormones	X		X		X	X	X	
Blood sample for pharmacokinetic assessment c			X		X	X	X	
Bone turnover markers			X				X	
Thromboembolic risk assessment	X							
Bilateral Doppler ultrasound of the lower extremities		X						
Assess hot flashes (electronic diaries)		X	X		X	X	X	
First dose			X					
Dispense study drug			X		X	X		
Collect capsule bottles (even if empty) and perform accountability/compliance assessment b					X	X	X	
Assessment of conmeds	X		X	X	X	X	X	
Assessment of AEs			X	X	X	X	X	X
Caprini VTE risk assessment d	X		X		X	X	X	

- a. Screening evaluations to be conducted within 28 days prior to Day 1.
- b. Collect capsule bottles (even if empty) and perform accountability/compliance assessment throughout the participation of the subject in the study.
- c. The pharmacokinetic blood samples should be done prior to receiving the dose of study drug for that day.
- d. It is important to note that it is expected that the patient population included in this study will have some risk of VTE due to age, presence of a malignancy, and BMI. The purpose of this assessment is a change in risk from baseline. Also, while the questionnaire is designed for the patient to complete, in this study, the Caprini VTE risk assessment should be filled out by study personnel with information from the patient and patient's chart.
- e. The same schedule of study evaluations will be used in Stage 1 and Stage 2 of this protocol.

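### The follow-up visit window lets the last scheduled adverse-event question fall up to 7 days before the 30-day SAE period ends

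*Protocol*

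**What the plan says.** **SAE period.** Protocol 8.13.4: "SAEs will be collected from the time of first study drug administration through 30 days after receipt of final dose of study drug". Protocol 8.13.3 agrees. Any SAE "which occurs during the study or within 30 days following cessation of study medication" must be reported, whether or not it is thought related to the drug. Under 8.13.4 the report is due "within 24 hours of the knowledge of the occurrence".

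**Last scheduled AE question.** Protocol 8.13 has AEs assessed at each clinic visit and also accepts spontaneous reports. In the schedule (Protocol Appendix B, copied in SAP 9.1) the row "Assessment of AEs" ends at the follow-up visit. No later visit or call is listed.

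**Timing of that visit.** Protocol 8.8 and SAP 4.7 set it at 30 days ±7 counted from the End of Study visit. Protocol 8.1 uses a different anchor and gives no window: "A follow-up visit will be conducted approximately 30 days after the last dose".

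**Last dose.** The dosing table in Protocol 7.3 runs to Day 84. For the PK samples, including Day 84, Protocol 8.9.1 says: "The sample should be taken prior to dosing with VERU-944 on these days". A man on schedule therefore takes his last dose on the day of his End of Study visit.

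**The concern.** The SAE period is counted from the last dose. The visit that closes active follow-up is counted from the End of Study visit and may be held a week early. A man and a site that both keep to the protocol can therefore have their last scheduled safety contact before the SAE period is over. The wording in 8.1 does not prevent this, because it sets no lower limit.

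What is at stake is a serious clinical event in the last days of the period that the site does not otherwise hear of, for example an admission to another hospital. The 24-hour reporting clock starts only when the site knows of the event, and after an early follow-up visit no planned contact remains to bring it to light. Thromboembolism is the most relevant case. The protocol has specific rules for men who become at high risk of it (8.10), scores Caprini risk repeatedly (Appendix B) and allows extra safety meetings about it (9.3.4.1). The trial has no formal data monitoring committee (9.3.4.1, SAP 6.8), so the Safety Review Team depends on complete SAE capture. The SAE tables in SAP 6.4.1 would also lack any such event.

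**Working it through.** **Inputs**
- SAE period: through post-dose day 30 (Protocol 8.13.3, 8.13.4).
- Follow-up visit: End of Study visit + 30 days, window −7 to +7 (Protocol 8.8, SAP 4.7), counted from the date the End of Study visit is held.
- d: days from last dose to the End of Study visit, taken as 0 or more because capsule bottles are collected at that visit (8.7).

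**The plan's own target.** Last dose Day 84, End of Study visit Day 84 (d = 0), follow-up Day 84 + 30 = Day 114. That is post-dose day 114 − 84 = 30, which matches 8.1 and the end of the SAE period. At the target there is no gap.

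**What the window permits**
- Earliest follow-up = d + 30 − 7 = post-dose day 23+d.
- Latest follow-up = d + 30 + 7 = post-dose day 37+d.
- Largest gap = max(0, 30 − (23+d)) = max(0, 7−d) days.
- Permitted days: from 23+d to 37+d, which is 15. Of these, max(0, 7−d) fall before post-dose day 30.

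| d | Earliest follow-up (post-dose day) | Largest gap (days) | Permitted days that leave no gap |
|---|---|---|---|
| 0 | 23 | 7 | 8 of 15 |
| 1 | 24 | 6 | 9 of 15 |
| 2 | 25 | 5 | 10 of 15 |
| 3 | 26 | 4 | 11 of 15 |
| 4 | 27 | 3 | 12 of 15 |
| 5 | 28 | 2 | 13 of 15 |
| 6 | 29 | 1 | 14 of 15 |
| 7 or more | 30 or later | 0 | 15 of 15 |

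**Worst case.** d = 0 and the first permitted day: 7/30 = 23% of the post-dose SAE period has no scheduled AE question.

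**Example.** Last dose Day 80, End of Study visit Day 84 (d = 4). Follow-up may be held from Day 107 to Day 121, which is post-dose day 27 to 41. The SAE period closes on Day 110, so the largest gap is 110 − 107 = 3 days.

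**After changing the window to −0/+7 with the same anchor.** Follow-up falls on post-dose day 30+d to 37+d. The earliest is never before day 30 for any d of 0 or more. Permitted days: 30 to 37 after the End of Study visit, which is 8.

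**The case against.** The best defence is that nothing in the documents conflicts. Sections 8.13.3 and 8.13.4 define which SAEs must be reported. They do not say that the last clinic contact must come on or after post-dose day 30. An SAE that becomes known must be reported with or without a visit, and spontaneous reports count. A reader might infer that SAE collection stops at an early follow-up visit, and the documents do not support that. What remains is narrower. A commitment to collect events through day 30 is weaker if the last planned question can come on day 23.

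The second defence is that a ±7 window is routine and the target date leaves no gap. Both are true. A gap needs the early side of the window, and even at d = 0, 8 of 15 permitted days leave none. The 23% is the extreme corner, not a typical value. The documents give no distribution of visit dates, so the number of SAEs missed cannot be estimated.

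Two stronger readings are tempting and should be resisted.

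- **Liver safety.** Because 8.11 has hepatic stopping rules, a reader might infer that a later follow-up visit would catch late liver signals. That visit comprises vital signs, physical examination and AEs only (8.8, SAP 4.7), and Appendix B lists no serum chemistry for it. Moving it would not detect a laboratory-only signal. It could pick up only a symptomatic event not already known to the site.
- **Men who leave early.** A reader might infer that they can go up to 30 days without a question. Sections 8.12 and 8.16 ask them for the End of Study evaluations, and 8.13 follows a man withdrawn for an AE until the outcome of that event is determined. The plan does not say whether or when the follow-up visit applies to early leavers, so any figure is an assumption. If the visit is timed from their End of Study evaluations, the gap is again up to 7−d days. If no visit is held, it is up to 30−d. If the visit is tied to nominal Day 84, the earliest date is Day 107, and there is no gap for a last dose on or before Day 77.

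**Conclusion.** The point holds as a minor gap in active SAE ascertainment. For a man whose last dose is 0 to 6 days before the End of Study visit, the permitted window can leave 7 down to 1 days of the SAE period without a scheduled AE question. There is no gap at the 30-day target or for d of 7 or more. The point matters mainly for thromboembolic and other clinical SAEs. It has no bearing on efficacy, alpha or power.

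The figures assume that follow-up is counted from the actual End of Study visit, that the visit is held, and that dosing does not continue after the End of Study visit. Whether 30 days is long enough given the drug's half-life is a separate question, which this point does not address. Severity: an optional change that the sponsor could make cheaply.

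**What to change.** In Protocol 8.8 and SAP 4.7, keep the End of Study visit as the anchor and change the window from ±7 to −0/+7 days, so that follow-up is held 30 to 37 days after the date of that visit. Align 8.1 with the same anchor and window. This removes only the early days of the present window, so nobody is seen earlier than the current 30-day target.

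Re-anchoring the visit to 30 to 37 days after the last dose would also close the gap, but it would bring follow-up forward for men with d above 0. At d = 10, for example, the current window is post-dose days 33 to 47, and re-anchoring would make it 30 to 37. For the same reason, an earlier scheduled visit should not be allowed to stand in for follow-up. If sites need the full 15-day window, a telephone AE enquiry at post-dose day 30 would serve instead.

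The cost is 8 permitted days instead of 15, and a protocol amendment under 10.3: at least notification of the ethics committees, and documented approval before implementation if it is classed as substantial. No visit is added.

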### **8.13.5 Precautions**

Adverse events should be treated in accordance with standard medical practice. During the course of the study, the overall safety, tolerability and pharmacokinetics of all study treatments will be reviewed by the sponsor and the investigator.

### **8.13.6 Reporting of Adverse Events Associated with Study Drug Overdose, Misuse, Abuse or Medication Error**

AEs associated with study drug overdose, misuse, abuse, and medication error refer to AEs associated with uses of the study drug outside of that specified by the protocol. Overdose, misuse, abuse, and medication error are defined as follows:

Overdose: Accidental or intentional use of the study drug in an amount higher than the protocol-defined dose

Misuse: Intentional and inappropriate use of study drug not in accordance with the protocol

Abuse: Sporadic or persistent intentional excessive use of study drug accompanied by harmful physical or psychological effects

Medication error: Any unintentional event that causes or leads to inappropriate study drug use or subject harm while the study drug is in the control of site personnel or the subject.

All AEs associated with overdose, misuse, abuse, or medication error should be captured on the Adverse Event eCRF and also reported using the procedures detailed in Reporting of SAEs even if the AEs do not meet serious criteria. Abuse is always to be captured as an AE. If the AE associated with an overdose, misuse, abuse, or medication error does not meet serious criteria, it must still be reported using the SAE form and in an expedited manner but should be noted as non-serious on the SAE form and the Adverse Event eCRF.

### **8.14 Concomitant Medications and Concomitant Therapies**

Any medication (including OTC medications) taken by a subject within 30 days prior to the Screening Visit and during the course of the study and the reason for use of the medication will be recorded on the eCRF. Upon entering the study, each subject will be instructed to report the use of any medication (including OTC medications) to the investigator.

Any radiation therapy (linear beam or seeds) taken by the subject within 30 days prior to the Screening Visit and during the course of the study, including type of treatment, and duration of the treatment will be recorded on the eCRF.

### **8.15 Prohibited Medications**

The following medications are prohibited with the appropriate washout period, if any, for each prohibited medication:

- All anabolic steroids and supplements containing anabolic steroids are prohibited from use during the study. This includes, but is not limited to, testosterone and testosterone-like compounds. Use of anabolic steroids and supplements containing anabolic steroids >6 months prior to screening into the study is allowed.
- Medroxyprogesterone acetate is prohibited from use during the study. Use of medroxyprogesterone >6 months prior to screening into the study is allowed.
- Clomiphene (Clomid® or a generic equivalent to Clomid) is prohibited from use during the study. Use of clomiphene >6 months prior to screening into the study is allowed.
- Diethylstilbestrol and estrogen therapy are prohibited from use during the study. Use of diethylstilbestrol and estrogen therapy >6 months prior to screening into the study is allowed.
- Initiation of treatment with selective serotonin reuptake inhibitors not allowed during the study and 6 months prior to the study is not allowed. However, if a patient is on stable sSSRI for >6 months prior to screening and is still qualifies for the study, this is allowed.
- Cytotoxic chemotherapy is prohibited from use during the study.
- Saw Palmetto, Black Cohosh, soy pills and PC-SPES are prohibited from use during the study. However, a washout period of >90 days prior to screening is allowed.
- Gabapentin is prohibited from use during the study. A washout period of >60 days from screening is allowed.
- Other experimental study medications are prohibited from use during the study. A washout of > 90 days prior to screening is allowed.

### **8.16 Withdrawal of Subjects**

- a. Any subject found to have entered the study in violation of the protocol will be withdrawn from the study.
- b. An effort must be made to determine why any subject discontinues the study prematurely. This information will be recorded on the case report form.
- c. All subjects reserve the right to withdraw from the study at any time. The investigator will encourage all subjects who decide to withdraw from the study to complete all evaluations which may be necessary to assure that the subject is free of untoward effects and to seek appropriate follow-up for any continuing problems.
- d. Any subjects who develop a clinically significant medical condition, as judged by the investigator, so that the subject no longer meets the inclusion/ exclusion criteria.
- e. Any subject who requires the use of an unacceptable concomitant medication will be withdrawn from the study.

The investigator will withdraw any subject from the study if, in the investigator's opinion, it is not in the subject's best interest to continue. No subject that discontinues from the study for any reason will be replaced.

The date the subject is withdrawn from the study and the reason for discontinuation will be recorded on the case report form. When a subject fails to return for scheduled study visits, the investigator will make a reasonable effort to contact the subject and determine why the subject failed to return. This information will be documented on the study records. When a subject is withdrawn from the study (regardless of the reason), all evaluations required at the final study visit should be performed.

## **9.0 STATISTICAL ANALYSIS**

### **9.1 Sample Size Calculation**

The proposed trial sample size,  $n=30$  per arm, total  $N=90$  in Stage 1, is based on the mean change in hot flash frequency from baseline to Week 4 (Day 28) (the planned primary endpoint at the time of the original study design). Other assumptions include: one-sided  $\alpha=0.10$ ;  $\beta=0.10$  (i.e., power=0.9), equal variances, the variance is equal to the mean of the active arm, and a frequency in at least one treated arm that is 40% less than that of the placebo arm on Week 4 (Day 28). The same assumptions hold for Stage 2 as well with proposed trial sample size of  $n=30$  per arm,  $N=60$  in Stage 2. Total enrollment if both stages are completed will be approximately  $N=150$ .

All patients in screening at the time that the 90th patient is randomized into Stage 1 of the study that qualify for the study will be randomized into the study up to a maximum of 120 patients (40 per arm). In Stage 2, all patients in screening at the time the 60th patient is randomized into Stage 2 of the study that qualify for the study will be randomized into the study up to a maximum of 80 patients (40 per arm).

